9.2 Analysis of secondary pharmacokinetic variables

No secondary pharmacokinetic variables will be analyzed in this trial.

9.3 Analysis of other pharmacokinetic variables

The other PK parameters for PSL metabolites ([REDACTED] and [REDACTED]) include:

- Single Dose Period: AUC_{0-t} , AUC , C_{max} , t_{max} , $t_{1/2}$, AUC_{0-12} , MR_{AUC} , $MR_{C_{max}}$
- Multiple Dose Period: $C_{max,ss}$, AUC_{τ} , t_{max} , $t_{1/2,ss}$, C_{trough} , $MR_{AUC_{\tau}}$, $MR_{C_{max,ss}}$

C_{max} and $C_{max,ss}$ will be determined from the observed concentration and time data. AUC_{τ} , AUC and AUC_{0-t} will be computed using the linear up/log down trapezoidal rule.

The other PK parameters for PSL include:

- Single Dose Period: CL/F , t_{max} , $t_{1/2}$, AUC_{0-12}
- Multiple Dose Period: CL_{SS}/F , t_{max} , $t_{1/2,ss}$, C_{trough} ,

- Bound and unbound plasma concentration of PSL will be analyzed in two samples. Results of analysis of bound and unbound plasma concentration of PSL will be presented in a different report, after final analysis will be provided.

CL/F and CL_{SS}/F will be determined from the observed concentration and time data.

The other PK parameters in urine of PSL and two of its metabolites ([REDACTED] and [REDACTED]) are: Ae, CL_R, fe (PSL only), MR_{Ae} and fe_{met} (metabolites only).

The other PK parameters and the amount of urinary excretion of PSL and its metabolites will be summarized by treatment period, cohort and nominal sampling times using descriptive statistics (number of available observations [n], arithmetic mean, median, standard deviation, minimum, maximum, geometric mean, geometric CV and 95% CI for the geometric mean [assuming lognormally distributed data]). Values below the LLOQ will be reported with a clear sign (flag variable in the dataset) indicating that they were below the LLOQ. t_{max}, t_{1/2}, and t_{1/2SS} will only display the number of available observations [n], median, minimum, and maximum.

The point estimate and the 95% CI for the median differences for t_{max} between the 2 cohorts (healthy participants and participants with moderate hepatic impairment) will be computed according to the Hodges-Lehmann method.

10.1 Extent of exposure

All study medication administration details will be listed by cohort and study participant. The listing will include the date and time of administration of the morning and evening dose and total daily dose of medication.

Exposure data will be listed only.

10.2 Adverse events

All AEs will be coded using the MedDRA® and characterized as pre-treatment and treatment-emergent according to the intake of the study medication. Adverse events with a start date prior to the first dose of study medication will be defined as pre-treatment AEs. A treatment-emergent AE (TEAE) is defined as any AE with a start date/time on or after the first dose of study medication or any unresolved event already present before administration of study medication that worsens in intensity following exposure to the treatment. Where dates are missing or partially missing, AEs will be assumed to be treatment-emergent, unless there is clear evidence to suggest that the AE started prior to the first dose of study medication. Missing or partially missing dates for AEs will be handled as described in Section 4.2.4.

Adverse events will be attributed to the treatment period in which they start. Thus, all AEs starting after the first intake of PSL through Day 7 will be attributed to Single Dose Period; all AEs starting after PSL intake on Day 8 through Day 18 will be attributed to the Multiple Dose Period and AEs starting more than 168 hours post last dose of PSL will attribute to the SFU Period.

All AEs will be recorded in the Case Report form (CRF) from the time of informed consent until study completion or termination. All AEs will be coded (see [Section 3.8](#)) and categorized by intensity (mild/moderate/severe) and relationship (related/not related) to study drug PSL as judged by the Investigator.

The number and percentage of participants who experience TEAEs will be summarized by MedDRA SOC, PT, treatment period and cohort.

Summaries of TEAEs will include the following:

- Overview of incidence of TEAEs (overview including number and percentage of participants with any TEAEs, any serious AEs, TEAE of Special Interest, TEAEs leading to discontinuation, drug-related TEAEs, severe TEAEs and TEAEs leading to death; event counts will also be included)
- Incidence of TEAEs by relationship
- Incidence of TEAEs by maximum intensity
- Incidence of non-serious TEAEs above reporting threshold of 5% of participants

Summary tables will contain counts of study participants, percentages of study participants in parentheses and the number of events where applicable. A participant who has multiple events in the same SOC and PT will be counted only once in the participant counts but all events will be included.

In summaries including relationship, the following relationships will be summarized: 'Not related', 'Related'. Participants who experience the same event multiple times will be included in the most related category for tabulations by maximum relationship. Events with missing relationship will be considered as 'Related' but recorded as missing in the listings.

In summaries including intensity, the following intensity categories will be summarized: 'Mild', 'Moderate', 'Severe'. Participants who experience the same event multiple times will be included in the most severe category for tabulations by maximum intensity. Events with missing intensity will be considered as 'Severe' events for summary purposes but recorded as missing in the listings.

Incidence of Non-Serious TEAEs above reporting threshold of 5% of participants will be reported by system organ class and preferred term.

Adverse event summaries will be ordered alphabetically by SOC and decreasing frequency of PT within SOC in the group column for tables including event counts. For tables including only number and percentage of study participants, summaries will be ordered alphabetically by SOC and decreasing incidence of PT within SOC in the group column.

Listings of AEs and TEAEs will include the following:

- All AEs
- Incidence of all TEAEs
- All Serious AEs
- Discontinuation due to AEs.

All listings (except incidence of all TEAEs) will be presented by study participant, treatment period and cohort and will include the onset date/time and outcome date/time of the event (including relative days), the event duration (derived), time to onset (derived), pattern of event, intensity, relationship, action taken, outcome and AEs that led to discontinuation. TEAEs and SAEs will be flagged.

The listing of incidence of all TEAEs will be presented by treatment period and will include intensity, relationship, severity, number of subject reporting a least one TEAE within SOC/PT, number of individual occurrences of TEAEs and site-participant number.

Additional summary tables of fatal, serious and discontinuation due to TEAEs by relationship will be produced if more than one of these events occurs.

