- ^a If a participant discontinues early, EOS procedures should be completed as the ETV. Upon early termination/withdrawal, the study participant will be encouraged to complete the Washout Period and complete EOS assessments following the last dose of study medication.
- ^b For convenience, the study participant may check-in to the clinic on the evening of Day -2. No study procedures will take place on Day -2. Study participants will be confined to the clinic from the time of check-in until check-out on Day 18.
- ^c All study participants will complete the “Screening/Baseline” version of the C-SSRS during Screening (assessing the past 6 months) and Baseline (Day -1), followed by the “Since Last Visit” version at subsequent visits.
- ^d Complete physical examinations will be performed on the days indicated. A brief physical examination will be conducted in a symptom-directed manner and only if clinically indicated (Section 8.4.1).
- ^e Vital signs should be taken pre the morning dose of Padsevonil and around the same time as the ECGs, i.e. 3 hours post the morning dose.
- ^f A serum pregnancy test will be performed for each WOCBP at Screening and a urine pregnancy test will be performed at any subsequent time points.
- ^g Laboratory safety assessments (hematology, chemistry, and urinalysis) will be performed before the morning dose of PSL.
- ^h 12-lead ECGs are taken 3 hours post the morning dose of Padsevonil. A 12-lead ECG will be performed after a rest of at least 5 minutes. All ECG recordings will be performed in triplicate and should be sufficiently separated so they have a different ‘minute’ on the timestamp, and all are done within 4 minutes.
- ⁱ Pharmacokinetic blood samples will be taken at the following time points: Predose and 15 minutes, 30 minutes, 45 minutes, 1h, 1.5h, 3h, 4h, 5h, 6h, 8h, 12h, 24h (Day 2), 48h (Day 3), 72h (Day 4), and 96h (Day 5) postdose. On Days 8, 9, 10, and 11, PK samples will be taken at predose. On Day 12, PK blood samples will be taken at the following time points: predose and 15 minutes, 30 minutes, 45 minutes, 1h, 1.5h, 3h, 4h, 5h, 6h, 8h, 12h, 24h (Day 13), 48h (Day 14), 72h (Day 15), and 96h (Day 16) postdose.
- ^j Two blood samples will be collected after multiple doses at steady state (Day 12 predose and 1.5h postdose [$\sim t_{max}$]) for PPB.

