3.2.2 Study periods

For each participant completing the study, the expected maximum duration of participation will be approximately 46 days with a maximum of 6 days exposure to investigational product, and will consist of the following periods:

- Screening/Baseline Period (Day -28 to Day -1)

The Screening Period consists of a single Screening Visit, which will be conducted at the unit within 28 days prior to check-in for treatment period, and a Baseline Visit, which will be conducted at the clinical research unit (CRU) 1 day prior to treatment period (on Day -1). Study participants will check-in at the CRU on Day -1.

- PSL Single Dose Administration Period (Day 1 to Day 7)

In the Single Dose Period, study participants will receive a single oral dose of 100mg PSL on Day 1, at approximately 8:00am, 30 minutes after a light meal has finished. No study drug will be administered on Days 2 to 7; assessments will be conducted during this time as specified in the Schedule of Activities (Table 2-). Days 2 to 7 are designated as a 6-day washout.

- PSL Multiple Dose Administration Period (Day 8 to Day 17)

In the Multiple Dose Period, study participants will receive multiple oral PSL doses on Days 8 to 12, followed by a 5-day washout (Days 13 to 17). Padsevonil will be administered BID, with one 100mg dose in the morning [approximately 8:00am] and one 100mg dose in the evening [approximately 8:00pm] on Days 8 to 11. One dose of 100mg of PSL will be administered on the morning of Day 12. The Follow-Up Period consists of an End of Study (EOS)/Early Termination Visit (ETV) performed after discharge on Day 18 or upon discontinuation of the study.

The end of the study is defined as the date of the last visit of the last participant in the study.

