6.4 Prior and concomitant medications

Prior medications include any medications that started prior to the date of first dose of PSL. Concomitant medications are medications taken after the first dose of PSL and/or the SFU Period. Concomitant medications will be attributed to the treatment period in which they start. Thus, any medication taken on Day 1 through Day 7 will be attributed to the Single Dose Period; any medications taken after the first dose of PSL on Day 8 through Day 18 (including SFU) will be attributed to the Multiple Dose Period.

If a medication starts prior to PSL administration and stopped after the first PSL administration or stopped during the Single Dose Period, then that medication will be classified as both prior and concomitant for Single Dose Period only. If a medication starts prior to PSL administration and is stopped during the Multiple Dose Period, then that medication will be classified as prior and concomitant for both Single and Multiple Dose Periods.

Any medications with missing dates and/or times will be handled as described in [Section 4.2.4](#) to classify them as prior or concomitant.

Prior and concomitant medications will be listed for all participants in the SS. Prior and concomitant medication will be tabulated separately. The summary will be presented by WHODD Anatomical Main Group [Level 1 term text], Pharmacological Subgroup [Level 3 term text] and PT. The reported term will be included in the listing. Tabulation for prior medications will be presented by cohort; tabulation for concomitant medications will be summarized by treatment period and by cohort.

All tabulations will be sorted alphabetically by Level 1 term, alphabetical Level 3 term within Level 1 and decreasing frequency of PT in the 'All Participants' column.

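### Adverse events starting on Day 8 before the morning dose have no period in SAP 10.2 and count as multiple-dose in SAP 3.2.2, so neither credits them to the single dose; SFU is undefined

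*SAP*

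**What the plan says.** SAP 10.2 starts from a principle, "Adverse events will be attributed to the treatment period in which they start", and then sets three windows:

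- **First window, for what follows the single dose:** "all AEs starting after the first intake of PSL through Day 7 will be attributed to Single Dose Period"
- **Second window, opened by dosing on Day 8:** "all AEs starting after PSL intake on Day 8 through Day 18 will be attributed to the Multiple Dose Period"
- **Third window, for late events:** "AEs starting more than 168 hours post last dose of PSL will attribute to the SFU Period"

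The same section tabulates TEAEs by treatment period and cohort, and Protocol 9.3.2 also asks for a breakdown by Treatment Period.

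Other sections draw the lines elsewhere. SAP 3.2.2 works in calendar days: a Single Dose Period of Days 1 to 7, then the "PSL Multiple Dose Administration Period (Day 8 to Day 17", with follow-up consisting of the EOS/ETV visit on Day 18. SAP 6.4, on concomitant medication, gives to the Multiple Dose Period "any medications taken after the first dose of PSL on Day 8 through Day 18 (including SFU", so SFU is part of that period there. SFU does not appear in the schedule (SAP Table 2-3), in the study periods of SAP 3.2.2, or in the abbreviation list, which has only FU.

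On timing, SAP 3.2.2 gives the single dose at about 08:00 on Day 1 and the multiple doses "with one 100mg dose in the morning [approximately 8:00am] and one 100mg dose in the evening [approximately 8:00pm] on Days 8 to 11". Safety laboratory tests are scheduled at Screening and on Days -1, 8, 12 and 18, and footnote g of Table 2-3 says "Laboratory safety assessments (hematology, chemistry, and urinalysis) will be performed before the morning dose of PSL".

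**The concern.** An event that starts on Day 8 before the morning dose follows the single dose and nothing else. It is treatment-emergent by the definition in SAP 10.2, yet it lies after the Single Dose window and before the Multiple Dose window. A programmer has to leave the period blank, fall back on SAP 3.2.2 and credit the event to a regimen not yet begun, or depart from the text and count it under the single dose. Different programmers could choose differently.

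The time slot also contains a scheduled assessment. Clinically relevant laboratory changes are recorded as AEs (Protocol 8.4.4). If such an AE is dated by the Day 8 sample, it lands in the gap.

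At the other end, SFU is named but not defined. It is a separate period in SAP 10.2 and part of the Multiple Dose Period in SAP 6.4. Day 18 itself is Multiple Dose in SAP 10.2 and follow-up in SAP 3.2.2. At stake is whether the by-period TEAE tables show which events followed the single dose and which followed repeated dosing.

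**Working it through.** The 168-hour limit has no derivation in the documents, so there is no planned figure to reproduce. The check is clock arithmetic on the SAP's own windows.

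**Inputs.** Doses at 08:00 and 20:00 on Days 8 to 11 and at 08:00 on Day 1 (SAP 3.2.2). The last dose is on the morning of Day 12; 08:00 is assumed from the earlier days. Day n runs from 00:00 to 24:00, and hours are counted from Day 1 00:00, so Day d at hour h is 24 × (d − 1) + h.

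**Gap on Day 8.**
- End of the Single Dose window: end of Day 7 = 24 × 7 = 168 h.
- Start of the Multiple Dose window: Day 8 08:00 = 24 × 7 + 8 = 176 h.
- Gap: 176 − 168 = 8 h, in every participant who goes on to Day 8.
- Time from the single dose to the first Day 8 dose: 176 − 8 = 168 h. The gap is therefore the last 8 hours of a 168-hour window after the single dose, the same length that SAP 10.2 allows after the last dose before an event moves to SFU.

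**Laboratory tests.** Of the post-dose tests on Days 8, 12 and 18, only Day 8 lies between the single dose and the first multiple dose. It is taken before dosing, so it falls at the pre-dose point that SAP 10.2 leaves unassigned.

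**The two readings of a Day 8 pre-dose event.**
- SAP 10.2 windows: no period.
- SAP 3.2.2 calendar days: Multiple Dose Period.
- Neither gives Single Dose Period.

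**End of study.** The Multiple Dose window closes at the end of Day 18 = 24 × 18 = 432 h. Overlap with SFU = 432 − (time of last dose + 168). A negative value is a gap.

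| Last dose | Hours | + 168 h | Overlap |
|---|---|---|---|
| Day 8 08:00 | 176 | 344 (Day 15 08:00) | 88 h |
| Day 9 08:00 | 200 | 368 (Day 16 08:00) | 64 h |
| Day 10 08:00 | 224 | 392 (Day 17 08:00) | 40 h |
| Day 11 08:00 | 248 | 416 (Day 18 08:00) | 16 h |
| Day 11 20:00 | 260 | 428 (Day 18 20:00) | 4 h |
| Day 12 08:00 (completer) | 272 | 440 (Day 19 08:00) | −8 h |

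Completers have no overlap but a second gap, Day 19 00:00 to 08:00, after discharge. The overlap of 4 to 88 h arises only for those who stop during Days 8 to 11, and SAP 10.2 does not say which rule takes precedence. A participant dosed only on Day 1 never enters the Multiple Dose window.

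**Would events be collected in the overlap?** SAP 4.4 asks early stoppers to attend EOS/ETV as soon as possible, and footnote a of Table 2-3 encourages them to complete the washout first. On the completers' spacing, Day 18 08:00 is 416 − 272 = 144 h after the last dose, before 168 h. SAP 10.2 records AEs until study completion or termination, so mainly late-reported SAEs would reach the overlap.

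**The case against.** The strongest reply is that the general principle in SAP 10.2 governs, that SAP 3.2.2 defines the periods, and that a Day 8 pre-dose event therefore does have a home. This stands in part: it shows that the fault is a conflict between two sections rather than an absence of any rule. It does not rescue the attribution, because that home is the Multiple Dose Period and no multiple dose has been given.

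Four stronger readings are tempting, and the documents do not support them.

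- A reader might infer that Day 8 is the only laboratory test after the single dose. Days 12 and 18 also have tests; Day 8 is the only one before repeated dosing begins.
- A reader might infer that the Multiple Dose and SFU windows overlap in general. For participants dosed as planned they do not, and for early stoppers the overlap would usually hold few events.
- A reader might infer that single-dose laboratory results are lost. SAP 10.3 summarises them by time point, so Day 8 stays identifiable. The SAP 10.2 windows govern AEs only. What is misleading is the heading: under SAP 3.2.2 the Day 8 pre-dose result sits in the Multiple Dose Period, and the Single Dose Period has no scheduled post-dose laboratory value.
- A reader might infer that the secondary endpoint is biased. That endpoint is TEAE incidence in the two cohorts. Overall counts are unaffected, both cohorts use the same windows, and no formal single- versus multiple-dose comparison is planned.

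It is also fair to say that no section fixes the onset of a laboratory AE at the sampling time. Whether such an event falls in the gap depends on how the investigator dates it.

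**Conclusion.** The point holds as a conflict in period attribution. Under SAP 10.2 about 8 hours of Day 8 belong to no period; under SAP 3.2.2 they belong to multiple dosing. Neither counts an event that followed the single dose under the single dose. SFU is undefined and inconsistent between SAP 6.4 and 10.2. Its conflict with the Day 18 limit is confined to participants who stop during Days 8 to 11 and are followed beyond 168 hours.

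The consequence is limited to descriptive by-period tables and listings. With about 12 participants per cohort, one reassigned participant moves a period percentage by 1/12 = 8.3 points. That is the weight of one participant, not an estimate of how often this will happen. The clock times assume dosing at about 08:00 and 20:00, including 08:00 on Day 12.

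The change is worth making because it is specific and nearly free, and because the current text would put real events under the wrong heading or under none.

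**What to change.** Use one set of dose-time boundaries in SAP 3.2.2, 6.4 and 10.2:

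- **Single Dose Period:** from the Day 1 dose up to, but not including, the first Day 8 dose, or to EOS/ETV if Day 8 is never dosed.
- **Multiple Dose Period:** from the first Day 8 dose to EOS/ETV.
- **Follow-up:** one defined window starting after EOS/ETV, with no overlap, replacing the 168-hour rule. Deleting SFU without a replacement would not do: Protocol 8.5.1 collects SAEs up to 30 days after each participant's end of study, and those would then have no period. The same section sets no time limit for SAEs thought to be related, so the window should say where later ones go.
- **Laboratory summaries:** label the Day 8 pre-dose results as following the single dose.
- **Missing onset time on Day 8:** state which period applies, since the boundary becomes a clock time.

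The cost is SAP wording and a few lines of programming. SAP Section 1 requires a SAP amendment when analysis definitions change before database lock. No additional data and no change to study conduct are needed.

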10.3 Clinical laboratory evaluations

Laboratory data (clinical chemistry, hematology and urinalysis) and changes from Baseline (if applicable) will be summarized by descriptive statistics at each time point by cohort and treatment period for both absolute values and changes from Baseline. Shift tables from Baseline to each post-Baseline time point will be presented by cohort. Any laboratory measurements that are BLQ or ALQ will be handled as described in [Section 4.2.2](#). Values outside the reference range for numeric variables will be flagged in the listings and in addition, will be listed separately. The reference ranges will also be reported in the listings.

A separate listing will present the study participant who meets one or more of the following criteria at any time point:

- Alanine aminotransferase (ALT) or aspartate aminotransferase (AST) increase $\geq 3x$ upper limit of normal (ULN)
- Total bilirubin increase $\geq 2xULN$
- Alkaline phosphatase $\geq 2xULN$

The listing will display only time points for which at least one of the above criteria was fulfilled for a given study participant, and will display all results obtained at time point for the specified variables

A summary of participants who meet the criteria for potential drug-induced liver injury (PDILI) will be presented together with any additional relevant data collected, if applicable.

Laboratory variables will be grouped according to the laboratory function panel ([Table 10-1](#)) and categorized as normal, high or low, if applicable, based on the reference range supplied by the analytical laboratory. For selected variables that are identified in [Table 10-1](#) the change in category from Baseline will be presented in a shift table at all post-Baseline time points.

Any additional laboratory variables not included in the outputs described previously will be listed separately. These will include:

- Serology
- Alcohol breath test
- Serum pregnancy test (for women of childbearing potential)
- Urine drug screen

Table 10-1: Safety Laboratory measurements

Laboratory Assessments	Parameters			
Hematology	Platelet Count	RBC Indices: MCV MCH Reticulocytes		WBC Count with Differential: Neutrophils Lymphocytes Monocytes Eosinophils Basophils
	RBC Count			
	Hemoglobin			
	Hematocrit			
	Coagulation panel			
	INR / Prothrombin			
Clinical Chemistry ^a	Blood Urea Nitrogen (BUN)	Potassium	Aspartate Aminotransferase (AST)/ Serum Glutamic-Oxaloacetic Transaminase (SGOT)	Total and direct bilirubin
	Creatinine	Sodium	Alanine Aminotransferase (ALT)/ Serum Glutamic-Pyruvic Transaminase (SGPT)	Total Protein
	Glucose	Calcium	Alkaline phosphatase	
Routine Urinalysis ^b	
 • Specific gravity, pH, glucose, protein, blood, ketones, bilirubin, urobilinogen, nitrite, leukocyte by dipstick. If protein or blood or leukocytes are abnormal (positive), a microscopic examination of the sediment will be performed. 			

Other Screening Tests	
 • Follicle-stimulating hormone (at Screening only) to confirm postmenopausal status in female study participants • Urine drug screen (to include at minimum: amphetamines, barbiturates, cocaine, opiates, cannabinoids and benzodiazepines) • Pregnancy test: Serum human chorionic gonadotropin (hCG) test (as needed for women of childbearing potential) • Serology (HIV 1 and 2 Ab, HBsAg, HCV-Ab) 
The results of each test must be entered into the eCRF.

-----------------------	---

^a Details of liver chemistry stopping criteria and required actions and follow up assessments after liver stopping or monitoring event are given in Section 7.1.1 and Section 10.6. All events of ALT $\geq 3 \times \text{ULN}$ and bilirubin $\geq 2 \times \text{ULN}$ ($>35\%$ direct bilirubin) or ALT $\geq 3 \times \text{ULN}$ and INR > 1.5 , if INR measured, may indicate severe liver injury (possible Hy's Law) and must be reported as an SAE (excluding studies of hepatic insufficiency or cirrhosis).

^b Local urine testing will be standard for the protocol unless serum testing is required by local regulation or IRB/IEC.

